3.3.4.3 Discontinuation of the trial by the sponsor

Boehringer Ingelheim reserves the right to discontinue the trial at any time for any of the following reasons (#5, #6 and #7 mandatory discontinuation criteria) :

1. Failure to meet expected enrolment goals overall or at a particular trial site
2. New toxicological findings, serious adverse events, or any safety information invalidating the earlier positive benefit-risk assessment.
3. Violation of GCP, or the CTP impairing the appropriate conduct of the trial.
4. The sponsor decides to discontinue the further development of the investigational product
5. Dose escalation in the SRD part or treatment in the BA part will be stopped if at least 2 subjects on active treatment at one dose level (SRD part) or 2 subjects in the BA part have relevant individual QT prolongations, i.e. a QTc increase of greater than 60 ms from baseline and/or an absolute QT or QTc greater than 500 ms, as confirmed by a repeat ECG recording.
6. Dose escalation in the SRD part will be stopped, if the C_{max} or AUC_{0-24} of at least 1 subject of one dose group increases above the following exposure thresholds or if the estimated gMean exposure is expected to exceed a C_{max} of 657 nM or an AUC_{0-24} of 6,201 nM*h. In this case, one or two additional dose levels lower than the planned next dose level may be given, as long as the expected gMean exposure values of the interim dose do not exceed these exposure thresholds. Estimation will be done based on preliminary PK results of preceding dose groups (see Section [7.4](#))
7. Occurrence of severe non-serious adverse events considered as drug-related by the investigator in 2 subjects of the same dose group (8 subjects) in the SRD part, or 3 subjects of the BA group (12 subjects), or occurrence of at least one drug-related serious adverse event. Moreover, dose escalation in the SRD part will be terminated if more than 3 of the actively dosed subjects at one dose level show drug-related and clinically relevant adverse events of at least moderate intensity.

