All ECGs will be recorded for a 10 sec duration after subjects have rested for at least 5 min in a supine position. ECG recording will always precede all other study procedures scheduled for the same time (except for blood drawing from an intravenous cannula that is already in place) to avoid compromising ECG quality.

Proprietary confidential information © 2020 Boehringer Ingelheim International GmbH or one or more of its affiliated companies

ECGs will be recorded as single ECGs or as triplicate ECGs (i.e. three single ECGs recorded within 180 sec) as indicated in the [Flow Charts](#).

ECGs may be repeated for quality reasons for instance due to alternating current artefacts, muscle movements, or electrode dislocation. For repetition within triplicate ECGs the time window of 180 sec applies as well. The repeat ECGs are assigned to the respective scheduled time point.

Additional (unscheduled) ECGs may be recorded for safety reasons. These ECGs are assigned to the prior scheduled time point in the sponsor's database.

Storing

All ECGs will be stored electronically on the Muse Cardiology Information System (█
█).

ECGs recorded during visit 2 of the SRD part will be evaluated by a central lab, while ECG recordings during the BA part will be only evaluated locally.

Data transfer

In the SRD part of the trial, for time points specified in the Flow Chart, ECGs will be transferred electronically to the central ECG lab █ for evaluation and/or storage except for ECGs from screening and EoTrial visits which will not be transferred.

In case of repeat ECGs due to quality reasons, only the repeated ECG recordings will be transferred to the central ECG lab, whereas the initially recorded ECGs will be discarded. Unscheduled ECGs (for safety reasons) will be transferred to the central ECG lab but will not be included into the statistical analysis of interval lengths.

Data transfer from the central ECG lab to the sponsor is described in the ECG data transfer agreement (see TMF).

Evaluation

a) Central ECG lab

Central ECG lab evaluation will be performed post-study for the first of three replicate ECGs per time point on Days 1 to Day 3 and for the single ECGs on Day 4 and 5. This will include the determination of cardiac QRS-axis as assessed by the ECG machine's algorithm as well as the intervals RR, PR, QRS and QT measured semi-automatically.

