Adverse events will be coded using the Medical Dictionary for Regulatory Activities (MedDRA). Frequency, severity, and causal relationship of AEs will be tabulated by treatment, system organ class and preferred term. SAEs, AESIs (see Section 5.2.6.1) and other significant AEs (according to ICH E3) will be listed separately.

Previous and concomitant therapies will be presented per treatment group without consideration of time intervals and treatment periods.

Laboratory data will be compared to their reference ranges. Values outside the reference range as well as possibly clinically significant values will be highlighted in the listings. Additionally, differences from baseline will be evaluated.

Vital signs or other safety-relevant data will be assessed with regard to possible on-treatment changes from baseline.

SRD part, only:

The ECG variables QT, HR, QTcF, QTcB, PR, QRS, and RR obtained from the centralised evaluation of 12-lead ECG recordings will be the basis for the derivation of quantitative and categorical ECG endpoints. These endpoints and their analyses will be described in the TSAP.

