6.7 BASELINE, TIME WINDOWS AND CALCULATED VISITS

SRD part: The baseline value is defined as the last measurement before first administration of trial medication (BI 474121 or Placebo).

BA part: The baseline value is defined as the last measurement before administration of trial medication in each treatment period (e.g. ptm -2:00).

For laboratory analysis, the last value on treatment will be defined as the last value during corresponding treatment period (usually 96:00h in first and second treatment period).

Adherence to time windows will be checked via the consistency check listings at the RPM.

Unscheduled measurements of laboratory data and vital signs data will be assumed to be repeat measurements of the most recent scheduled measurement (e.g. for follow-up or confirmation of a particular value). Therefore, unscheduled measurements will be assigned to the planned time point of the previous scheduled measurement.

There will be a centralised evaluation of the 12-lead ECG recordings of the SRD part at the time points and for the ECG recordings specified in [Table 6.7: 1](#) below:

Table 6.7: 1 Time schedule of 12-lead ECG recordings (SRD part)

Visit	Day	Planned time [hh:mm] (relative to drug administration)	Study phase	Central evaluation
1	-21 --1		Screening	NA
2	1	-01:00	Baseline	first ECG of each of the 3 triplicate baselines
		-00:45		
		-00:30		
		00:30		
		01:00		
		01:30		
		02:00		
		03:00		
		04:00		
		06:00		
		08:00		
		12:00		
	2	24:00		
		34:00		
	3	48:00	On-treatment	first single ECG of the triplicate
	4	72:00		
	5	96:00		
5	8-15		End-of-study examination	NA

At Screening and End-of-study examination ECG recordings are performed as single ECGs and will not be transferred to central ECG lab. Three triplicate ECGs will be recorded as the baseline before the first drug administration, but only the first ECG of each of the 3 baseline triplicates will be transferred to the database. At all other time points, 1 triplicate ECG will be recorded, but only the first single ECG of the triplicate will be transferred to the database. The baseline value of an ECG variable is defined as the mean of the ECG variable values prior to drug administration.

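### SRD part: unscheduled safety ECGs are excluded from the interval analysis with no exception for categorical QT/QTc endpoints, so a prolongation seen only on such an ECG may go uncounted

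*Protocol*

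**What the plan says.** Protocol 5.2.5.1 separates three kinds of recording in the SRD part.

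- **Scheduled ECGs.** "Central ECG lab evaluation will be performed post-study for the first of three replicate ECGs per time point on Days 1 to Day 3", together with the single ECGs on Days 4 and 5.
- **Repeats for technical quality.** Here "only the repeated ECG recordings will be transferred to the central ECG lab, whereas the initially recorded ECGs will be discarded".
- **Extra safety ECGs outside the schedule.** In the sponsor's database, "These ECGs are assigned to the prior scheduled time point". They also go to the central lab, but they "will be transferred to the central ECG lab but will not be included into the statistical analysis of interval lengths".

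Protocol 7.3.4 says that the centrally evaluated ECG variables, including QT and QTcF, "will be the basis for the derivation of quantitative and categorical ECG endpoints", and leaves the details to the SAP.

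SAP 7.8.4 plans frequency tables for the categorical endpoints. It also plans an end-of-text listing with time profiles for every subject who has a notable interval finding. SAP 6.6 refers to new-onset QT/QTc categories and to Appendix 10.1.3, which is not in the text available. SAP 6.7 gives a rule for unscheduled values, but only for other data: "Unscheduled measurements of laboratory data and vital signs data will be assumed to be repeat measurements" of the preceding scheduled one. SAP section 4 declares one change from the protocol, about where protocol-deviation categories are kept.

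**The concern.** Leaving unscheduled ECGs out of means by planned time and out of exposure-response models is sound. Those analyses need a common time grid, and recordings triggered by a clinical worry would distort it.

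Categorical QT/QTc endpoints do a different job: they identify individual subjects with a large value. An ECG taken because something looked wrong is among the recordings most likely to show one. As worded, the exclusion reaches any analysis of interval lengths, and QT/QTc categories are analyses of interval lengths.

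If a subject's only prolongation is on an unscheduled ECG, the blinded central measurement does not feed the counts. The event is then visible in the tables only if the investigator judges it clinically relevant and reports it as an adverse event. This matters here because protocol 1.3.2.2 names waiving a thorough QT trial as one possible use of the exposures reached in the SRD part.

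**Working it through.** The plan states no figure on this point, so the check compares texts and adds two short counts.

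**1. How far the exclusion reaches.** Protocol 5.2.5.1 excludes unscheduled safety ECGs from the interval analysis and lists no exception. Protocol 7.3.4 derives quantitative and categorical endpoints from the same central measurements. SAP section 4 says the protocol's analyses will be performed and declares no ECG change. SAP 6.7 covers unscheduled laboratory values and vital signs, not ECGs. On the visible text, the exclusion stands for categorical endpoints too.

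**2. What is read centrally.** Inputs: SAP Table 6.7: 1 for time points; protocol SRD flow chart, footnote 10, for triplicate or single recording.

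- Post-dose time points from 0:30 to 48:00 h: 0:30, 1:00, 1:30, 2:00, 3:00, 4:00, 6:00, 8:00, 12:00, 24:00, 34:00, 48:00 = 12, in triplicate: 12 × 3 = 36 recordings.
- 72:00 and 96:00 h, single: 2 recordings.
- Scheduled post-dose recordings: 36 + 2 = 38.
- Centrally measured: 12 + 2 = 14, and 14/38 = 36.8%.
- Not measured: 38 − 14 = 24, all second or third replicates. That loss comes from the first-replicate rule, not from the exclusion discussed here.

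**3. Where an event could fall between scheduled ECGs.** Gaps after 12 h: 24 − 12 = 12 h; 34 − 24 = 10 h; 48 − 34 = 14 h; then 24 h and 24 h. A transient prolongation in one of these gaps could be recorded only on an unscheduled ECG.

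**4. Which prolongations are lost.**

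| Where the prolongation is seen | Counted under the visible text? |
|---|---|
| Central reading of a first replicate or a Day 4–5 single ECG | Yes, whether or not a later repeat is included |
| Quality repeat that replaces a first replicate or single ECG | Yes; quality repeats are not excluded |
| Only on a second or third replicate | No, because of the first-replicate rule |
| Only on an unscheduled safety ECG | Not under protocol 5.2.5.1; the SAP's category definitions are not visible |

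The last row is the point made here.

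**5. Treatment of other safety data.** Unscheduled laboratory and vital-sign values are assigned to the previous planned time (SAP 6.7). Laboratory summaries then use the worst value at that time (SAP 7.8.2), and vital signs use the last (SAP 7.8.3). Unscheduled ECGs are also assigned to the prior time point, but are then left out.

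**6. Size.** Each dose group has 6 subjects on active drug. The documents do not say how many unscheduled ECGs to expect. Assuming 0, 1 or 2 affected subjects in a group, the understatement is 0/6 = 0%, 1/6 = 16.7% or 2/6 = 33.3%. Over all planned active subjects (7 × 6 = 42), one subject is 1/42 = 2.4%. This shows the scale; it does not estimate how often the case arises.

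**The case against.** The strongest case for the present rule is ascertainment. SRD investigators know who receives active drug (protocol 4.1.5.1) and decide when to record an extra ECG. Counting those ECGs in a subject-level maximum gives some subjects more chances to cross a threshold, and could inflate active counts relative to placebo. This stands, and it is why the fix shows the counts both ways. It does not justify having no count that includes these ECGs.

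A second objection is that the SAP's definitions of categorical QT endpoints and notable findings are not visible, so the SAP may already bring unscheduled ECGs in. That also stands as a limit, and the missing text is no fault of the plan. The protocol sentence is nevertheless explicit, and SAP section 4 declares no departure from it. It is also open to argument whether a listing is a statistical analysis at all, so the effect on the notable-finding display is only possible.

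A reader might infer more than the documents support:

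- **That any prolongation confirmed on a repeat drops out.** Stopping criterion 5 in protocol 3.3.4.3 needs a prolongation "as confirmed by a repeat ECG recording", so an earlier ECG exists. If that was a scheduled first replicate or a Day 4–5 single ECG, and the central reading agrees, the subject is counted without the repeat.
- **That the report could show no prolongation where escalation was stopped for one subject.** The criterion requires at least two subjects on active drug at one dose level. In-study cardiac safety uses local QT and QTcB values, while the reported summaries use central QT and QTcF, so the two could differ whatever is done with unscheduled ECGs. Clinically relevant findings, central or local, also become adverse events and are tabulated.
- **That the BA part is affected.** Its ECGs are evaluated locally only, and the SAP's ECG evaluations cover the SRD part.

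**Conclusion.** The concern holds in a narrow form, for the SRD part only. A QT/QTc prolongation that appears on an unscheduled safety ECG and on none of the 14 centrally read scheduled post-dose ECGs may be absent from the categorical counts. It may also fail to trigger the notable-finding display. It would then reach the report's tables only as an adverse event, through an unblinded judgement.

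The conclusion assumes that the unseen SAP appendix does not override the protocol. How often the case would arise is unknown and may be zero; where it does, each such subject moves a dose-group incidence by 1/6. The documents do not show that the counts will in fact be biased. They show that a stated rule allows a gap in the endpoint meant to find individual subjects, and that it is cheap to close.

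**What to change.** - **Protocol 5.2.5.1:** limit the exclusion of unscheduled safety ECGs to descriptive statistics by planned time and to the exposure-response models.
- **SAP 7.8.4:** state that unscheduled safety ECGs are centrally measured under the same blinded procedure and count in the subject-level categorical QT/QTc summary and in the notable-finding listing. Show the categorical summary with and without them, because unblinded investigators decide when they are recorded.
- **SAP section 4:** declare this as a change from the protocol. If SAP Appendix 10.1 already includes these ECGs, only the alignment of protocol 5.2.5.1 and the declaration are needed.

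The cost is about one sentence in each place, one extra version of the categorical table, and central measurement of the few recordings already transferred. No ECG is added, and the stopping criteria and the decision to record an unscheduled ECG are unchanged.

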CL/F	Apparent clearance of the analyte in plasma after extravascular administration
CL _{R, t1-t2}	Renal clearance of the analyte in plasma from the time point t ₁ to t ₂
C _{max}	Maximum measured concentration of the analyte in plasma
C _{min}	Minimum measured concentration of the analyte in plasma
CML	Clinical Monitor Local
CRF	Case Report Form, paper or electronic (sometimes referred to as 'eCRF')
CTP	Clinical trial protocol
CTR	Clinical trial report
CV	Arithmetic coefficient of variation
DILI	Drug induced liver injury
ECG	Electrocardiogram
eCRF	Electronic case report form
eDC	Electronic data capture

Proprietary confidential information © 2020 Boehringer Ingelheim International GmbH or one or more of its affiliated companies

EDTA	Ethylenediaminetetraacetic acid
EoTrial	End of trial
EudraCT	European Clinical Trials Database
F	Absolute bioavailability factor
$f_{e_{t_1-t_2}}$	Fraction of administered drug excreted unchanged in urine over the time interval from t_1 to t_2
GCP	Good Clinical Practice
gCV	Geometric coefficient of variation
GI	Gastro-intestinal
gMean	Geometric mean

HR	Heart rate
IB	Investigator's brochure
IEC	Independent Ethics Committee
IPD	Important Protocol Deviation
IRB	Institutional Review Board
ISF	Investigator site file
λ_z	Terminal rate constant of the analyte in plasma
LC-MS/MS	Liquid chromatography with tandem mass spectrometry
MDA	Methylenedioxymethamphetamine
MDMA	Methylenedioxymethamphetamine
MedDRA	Medical Dictionary for Regulatory Activities
MRT _{ex}	Mean residence time of the analyte in the body, extravascular
PD	Pharmacodynamic(s)
PE	Polyethylene
PfOS	Powder for reconstitution of an oral solution
PIB	Powder in the bottle
PK	Pharmacokinetic(s)
PKS	Pharmacokinetic set
PP	Polypropylene
PR	Pulse rate
PTS	Peak-trough swing
QT	Time between start of the Q-wave and the end of the T-wave in an electrocardiogram
QTc	QT interval corrected for heart rate using the method of Fridericia (QTcF) or Bazett (QTcB)
R	Reference treatment
REP	Residual effect period
RR	Respiratory rate

Proprietary confidential information © 2020 Boehringer Ingelheim International GmbH or one or more of its affiliated companies

[figure not shown]
SAE	Serious adverse event
SCR	Screening
SOP	Standard operating procedure
SRD	Single-rising dose
ss	(at) steady state
T	Test product or treatment
TMF	Trial master file
$t_{1/2}$	Terminal half-life of the analyte in plasma
t_{\max}	Time from (last) dosing to the maximum measured concentration of the analyte in plasma

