The dose groups will be dosed consecutively in ascending order, and a time interval of at least 3 days will be maintained between the last drug administration to subjects in the previous dose group and the first drug administration to subjects in the subsequent dose group. Moreover, a time interval of at least 7 days will be maintained for DG 1 to 3 and 14 days for DG 4 to 7 between the first drug administration to subjects in the previous dose group and the first drug administration to subjects in the subsequent dose group. The decision to treat the next dose group will be based upon safety, tolerability and pharmacokinetic data (for details refer to Section [7.4](#)) of the preceding dose groups. The next dose group will only be treated if, in the opinion of the investigator, no safety concerns have arisen in the preceding dose groups (i.e. no dose-limiting events occurred), and if none of the pre-specified trial-specific stopping criteria have been met (refer to Section [3.3.4.2](#)).

A documented safety review must take place prior to each dose escalation. Furthermore, an unscheduled safety review meeting can be requested anytime by the Principal Investigator (or an authorised deputy) or the sponsor of the study (for instance, due to the occurrence of any unforeseen adverse events).

Although no formal Safety Review meeting will take place within a given dose group, safety will be continuously monitored during this trial, and an individual will only be dosed in the absence of any safety concern (i.e. no dose-limiting events occurred) and if none of the pre-specified trial-specific stopping criteria have been met (refer to Section 3.3.4.2).

At minimum, data from 4 subjects on active drug need to be available for escalation to a higher dose. For the minimum dataset with regards to preliminary PK data, see Section 7.4. The minimum data set for review consists of the following:

- AEs in the current and preceding dose groups up to at least 48 h post dosing, including clinically relevant findings from ancillary safety testing listed below (Note: AEs may be ongoing at the time of Safety Reviews and AE information may be subject to change prior to Database Lock)
- Results from 12-lead ECG and continuous ECG monitoring in the current and preceding dose groups up to at least 24 h (DG 1 to 3) or 48 h (DG 4 to 7) post dosing
- Vital signs and results from the orthostatic tests in the current and preceding dose groups up to at least 24 h post dosing

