For the inclusion or exclusion (see Section [3.3](#)) of a subject and for the assessment of cardiac safety during the study, the QT and QTcB values generated by the computerised ECG system or their manual corrections by the investigators will be used. In doubtful cases (SRD part), ECGs may be sent upfront (i.e. prior to the regular data transfer) for cardiologic assessment by the central lab. In this case, these centrally measured results would overrule any other results obtained.

Abnormal findings, irrespective of whether they originate from central or local evaluation, will be reported as AEs (during the trial) or baseline conditions (at screening) if judged clinically relevant by the investigator. Any ECG abnormality will be monitored carefully and, if necessary, the subject will be removed from the trial and will receive the appropriate medical treatment.

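### The mandatory QTc stop runs in effect on QTcB, while the SAP's main QT metric is QTcF, so when heart rate falls a QTcF increase above 60 ms need not meet it

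*Protocol*

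**What the plan says.** - **Stopping rule.** Protocol 3.3.4.3 marks "5, #6 and #7 mandatory discontinuation criteria". Under #5, SRD escalation or BA treatment stops once two subjects (on active treatment at one SRD dose level, or in the BA part) show "a QTc increase of greater than 60 ms from baseline and/or an absolute QT or QTc greater than 500 ms", confirmed by a repeat ECG. No correction is named there, and the abbreviation list lets QTc mean Fridericia or Bazett.
- **On-study values.** Protocol 5.2.5.1, Evaluation b), covers eligibility and on-study safety: "for the assessment of cardiac safety during the study, the QT and QTcB values generated by the computerised ECG system", or the investigators' manual corrections, are used.
- **Central reading.** In the SRD part, "Central ECG lab evaluation will be performed post-study for the first of three replicate ECGs per time point". There is an early route: "In doubtful cases (SRD part), ECGs may be sent upfront (i.e. prior to the regular data transfer) for cardiologic assessment by the central lab", and that result then overrules. For the BA part, "ECG recordings during the BA part will be only evaluated locally".
- **Escalation review.** The minimum data set in Protocol 3.1 includes "Results from 12-lead ECG and continuous ECG monitoring in the current and preceding dose groups". The Principal Investigator and the Clinical Trial Leader must both be free of safety concerns before the dose is raised.
- **Analysis.** SAP 7.8.4 gives descriptive statistics for QTcF and takes its change from baseline as the response in the concentration model. QTcB appears in listings only. The check of the heart-rate correction is on QTcF against RR. The same concentration analyses are repeated for heart rate.

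**The concern.** Criterion #5 is there so that a large individual prolongation stops a first-in-human escalation without further discussion. On study it is read on one correction, and afterwards the drug's QT effect is judged on another. If heart rate stays put, the difference is a few milliseconds. If it moves within a subject, the gap grows, and the direction matters. A rise makes the stop earlier in QTcF terms, which is cautious. A fall makes it later, so a subject can pass +60 ms on the sponsor's own main metric and not be counted. The SAP models heart rate against concentration, so a drug effect on heart rate is something the sponsor itself intends to examine.

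**Working it through.** The 60 ms limit is a rule, so there is no plan figure to reproduce. The question is what the rule amounts to in QTcF.

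**Inputs from the documents:** the limits of 60 ms and 500 ms (Protocol 3.3.4.3 #5) and the 50 to 90 bpm pulse range at entry (Protocol 3.3.3).

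**Assumed:** baseline QTcF of 400 ms, with 380 and 420 ms as the range, and the heart-rate shifts.

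**Formulas**, with RR = 60/HR in seconds:

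- QTcB = QT/RR^(1/2) and QTcF = QT/RR^(1/3), so QTcB = QTcF × k, where k = (HR/60)^(1/6).
- k is 1.0000 at 60 bpm, 1.0134 at 65, 1.0260 at 70 and 1.0491 at 80.
- QTcF increase at which QTcB has risen by 60 ms = (QTcF0 × k0 + 60)/k1 − QTcF0, where 0 is baseline and 1 is on treatment.

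For 70 to 60 bpm: (400 × 1.0260 + 60)/1.0000 − 400 = 70.4 ms.

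| Heart rate, bpm | QTcF0 380 | QTcF0 400 | QTcF0 420 |
|---|---|---|---|
| 65 to 60 | 65.1 | 65.4 | 65.6 |
| 70 to 60 | 69.9 | 70.4 | 70.9 |
| 80 to 60 | 78.7 | 79.6 | 80.6 |
| 60 to 65 | 54.2 | 53.9 | 53.6 |
| 60 to 70 | 48.8 | 48.3 | 47.8 |
| 60 to 80 | 39.4 | 38.5 | 37.5 |

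With no change in heart rate the figure is 61.9 ms at 50 bpm, 58.5 at 70 and 56.1 at 90.

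**How much of a fall is needed.** The limit is looser than +60 ms QTcF when QTcF0 × (k0 − k1) > 60 × (k1 − 1). Any fall that ends at 60 bpm or below satisfies this. A fall that ends higher must be large enough. To end at 70 bpm with QTcF0 400, k0 must exceed 1.0260 + 60 × 0.0260/400 = 1.0299, which is a start above 60 × 1.0299^6, about 71.6 bpm.

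**A subject the rule would miss.** QTcF goes from 400 to 465 ms (+65) as heart rate falls from 70 to 60 bpm.

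- QTcB goes from 400 × 1.0260 = 410.4 to 465.0, an increase of 54.6 ms, so the +60 ms limb is not met.
- QT goes from 400 × (60/70)^(1/3) = 380.0 to 465.0, up 85 ms. Neither QT nor QTcB is above 500, so #5 is not met at all.

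**The 500 ms limb.** QTcF always lies between QT and QTcB, because its RR exponent of 1/3 lies between 0 and 1/2. A QTcF above 500 ms therefore implies that QT (below 60 bpm) or QTcB (above 60 bpm) is above 500 ms, so this limb loses nothing as written. It also closes some of the gap. For 60 to 50 bpm with QTcF0 400, the +60 ms limb on QTcB is reached only at +74.2 ms QTcF, but QT reaches 500 ms at QTcF = 500/(60/50)^(1/3) = 470.5, or +70.5 ms. For 80 to 60 bpm with QTcF0 420, QT is about 501 ms at the point where QTcB reaches +60 ms.

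**Heart rate alone.** With QTcF fixed at 400 ms, a start at 60 bpm needs 60 × (460/400)^6, about 139 bpm, to add 60 ms to QTcB (134 to 145 bpm for baselines of 420 to 380 ms).

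**The case against.** The strongest reply is that the formula is not missing. Section 5.2.5.1 b) fixes QTcB for on-study cardiac safety, a local real-time rule and a post-study model do different jobs, and nothing requires one metric for both. That stands in part. A reader might infer that #5 has no defined correction, or that protocol and SAP contradict each other. The documents do not support either. What #5 lacks is a cross-reference.

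Secondly, "looser" is true only in QTcF terms, and a QTcF rule would vary in the same way in QTcB terms. That also stands. QTcF is not shown to be the right correction for these subjects; the SAP plans to check it on trial data. The point is narrower: the sponsor's own main metric can pass the limit without being counted.

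Thirdly, simply replacing QTcB by QTcF, as a reader might propose, would relax the rule elsewhere. QTcB 500 ms equals QTcF of about 487 ms at 70 bpm, 477 at 80 and 467 at 90, so the QTc >500 ms limb would act later above 60 bpm. With a rise from 60 to 80 bpm, the +60 ms limb would move from +38.5 to +60 ms QTcF. This objection is decisive against replacement, but not against adding QTcF.

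Lastly, the gap is narrow and partly covered. ECGs are supine and rested, a 5 bpm fall costs about 5 ms, and two subjects are needed. An 85 ms rise in QT could be noticed at review or sent for early central reading. SAP 7.8.4 flags notable ECG findings and gives those subjects a separate listing. In the BA part, the dose must be at most a quarter of one already tolerated in the SRD part, and each period has 12-lead ECGs only pre-dose and at 24 h. All of this limits the consequence. However, apart from the 500 ms limb, the on-study safeguards against an uncounted QTcF rise depend on judgement, the SAP listings are not a stopping rule, and early central reading is offered only in the SRD part.

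**Conclusion.** The concern holds in a limited form. Criterion #5 is in effect a QTcB rule, and when heart rate falls it can leave uncounted a subject whose QTcF has risen by more than 60 ms. With baseline QTcF at 400 ms, the uncounted band runs from +60 to about +65 ms for 65 to 60 bpm, to +70 ms for 70 to 60, and to +80 ms for 80 to 60. Baselines of 380 or 420 ms move these by about 1 ms at most.

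The result rests on assumed baselines and illustrative shifts, since the documents report no within-subject heart-rate change. It also rests on reading 5.2.5.1 b) as governing #5, which that section does not cite. The SAP's detailed QTc category definitions (Section 10.1) are not in the available text and could not be checked.

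A reader might also infer that heart rate by itself would trigger the stop. At resting rates it would not. This is a weakness in a mandatory safety rule that should be closed because it is cheap to close, not evidence that subjects are unprotected.

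**What to change.** In Protocol 3.3.4.3 #5 and 5.2.5.1 b):

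- Have the site compute QTcF alongside QTcB from the same QT and RR (machine-generated or manually corrected).
- Count a subject if either QTcF or QTcB rises by more than 60 ms from baseline, or if QT, QTcF or QTcB exceeds 500 ms. Naming QTcF in the 500 ms limb adds no subjects; it only makes the wording complete.
- Correct and read baseline and on-treatment values the same way. If a central reading overrules, take both from the central reading.
- Keep the repeat-ECG confirmation and the two-subject count.

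The cost is protocol wording and one extra calculation from QT and RR, which QTcB already needs. In the rare overruled SRD case, pre-dose ECGs already due for central reading would be read earlier. No recordings are added. The downside is that slightly more subjects may meet the criterion, through the +60 ms limb.

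If the sponsor prefers QTcF alone, the protocol should state that this relaxes the QTc >500 ms limb at heart rates above 60 bpm and the +60 ms limb when heart rate rises.
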